2.2 Immune Checkpoint Therapy

In the process of tumor occurrence and development, tumor cells undergo many hereditary and epigenetic changes compared with normal cells, and theoretically have enough antigens to be recognized by the human immune system, which can trigger an immune response to inhibit tumor growth. However, tumors can suppress the immune response through multiple pathways to evade the attack from immune system^[20].

In the process of effective anti-tumor immunity, T cells as core executors are first recognized by antigen recognition signals mediated by T cell receptor (TCR), while numerous costimulatory signals and coinhibitory signals finely regulate the intensity and quality of T cell responses^[21], of which the inhibitory signal is the checkmate inhibitor. Under physiological circumstances, these immune checkpoints are involved in maintaining immune tolerance to self-antigens on the one hand to avoid autoimmune diseases; on the other hand, they can avoid tissue damage caused by excessive activation of immune responses^[22]. However, tumor cells can use these immune checkpoints to inhibit T cell activation, thereby evading immune killing.

2.2.1 PD-1/PD-L1 and tumors

The induction of effective anti-tumor immune responses is a complex process involving multiple steps. The key step depends on the ability of the major executor, effector T-cells, to effectively recognize and kill tumor cells, while the activation of T-cells is the premise for their anti-tumor effects.

Programmed death-1 (PD-1) is one of the many immune checkpoints that can inhibit T cell activation. It is one of the important inhibitory receptors on the surface of T cells and is homologous with CD28 and CTLA-4. It is named for its initial discovery in apoptotic T cell lymphoma and its ability to promote programmed cell death. PD-1 is expressed on activated T cells, depleted T cells, activated B cells, natural killer cells, dendritic cells, and activated monocytes, but not on the surface of resting lymphocytes^[23,24]. Up-regulation of PD-1 expression on the surface of activated lymphocytes can lead to inhibition of acquired or innate immune responses, as PD-1-mediated immunosuppression can be triggered when the phosphorylase binds to the immunoreceptor tyrosine-based inhibitory motif and conversion motif of PD-1 in the cytoplasm^[23]. PD-1 has two major ligands, programmed death factor ligand 1 (PD-L1 [B7-H1]) and programmed death factor ligand 2 (PD-L2 [B7-DC])^[25,26].

The PD-1/PD-L1 binding plays an important role in regulating T cell activation and maintaining peripheral immune tolerance (the role of PD-1 in the process of T cell activation, aging, and response is shown in [Figure 1](#) below^[8]). When T cells do not express PD-1, they interact with antigen-presenting cells to activate and proliferate T cells and secrete activated cytokines to act on tumor cells, mainly manifested as killing of tumor cells (Figure 1A); activated T cells begin to express PD-1, and when they bind to ligand PD-L1 on antigen-presenting cells or tumor cells, the inhibitory signals transmitted by PD-1 will inhibit the proliferation of T cells and the secretion of active cytokines, so that the function of T cells is reduced, and most tumor cells evade immune cell attack through this mechanism (Figure 1B); if the interaction between PD-1 and PD-L1 is blocked by drugs, the activity of T cells and the ability to kill cancer cells can be restored (Figure 1C)^[27].

[figure not shown]

Figure 1. PD-1's role in T cell activation, aging, and response

2.2.2 Anti-PD-1/PD-L1 agents

PD-L1 is widely expressed in solid tumors and hematological tumors ([Table 3](#))^[28]. A variety of tumor types rank among the top ten in incidence/mortality in China, such as lung cancer, colon cancer, gastric cancer, esophageal cancer, breast cancer, and liver cancer^[29]. Anti-PD-1 agents play a therapeutic role by blocking the binding of PD-L1 on tumor cells and PD-1 of T cells, blocking its inhibition on T cells. Compared with traditional cytotoxic chemotherapy, PD-1 targeted therapy has higher specificity, lower toxicity, and applicability to a variety of tumor types.

Table 3. PD-L1 expression in multiple types of tumors

Types of Tumors	Positive Rate of PD-L1 (%)
Malignant glioma	100
Nasopharyngeal Carcinoma	68-100
Melanoma	40-100
Bladder cancer	28-100
Non-Small Cell Lung Cancer	35-95
Small Cell Lung Cancer	28.6%
Multiple Myeloma	93
Hepatic Cancer	45-93
Ovarian Cancer	33-80
Colon Cancer	53
Gastric Cancer	42
Esophageal Cancer	42
Pancreatic Cancer	39
Breast Cancer	31-34
Renal Cancer	15-24
Lymphoma	17-94
Leukaemia	11-42

Note: * The data comes from the 2016 World Conference on Lung Cancer.

See [Table 4](#) for anti-PD-1/PD-L1 monoclonal antibodies that have been marketed as of 27 Sep., 2017.

Table 4. Marketed anti-PD-1/PD-L1 monoclonal antibodies

Generic Name (Trade Name)	Company	Target	Category	Time of Marketing	Current Indication(s)
Nivolumab (OPDIVO)	BMS	PD-1	IgG-4	2014	Melanoma, non-small cell lung cancer, renal cell carcinoma, classic Hodgkin's lymphoma, head and neck squamous cell carcinoma, urothelial carcinoma, colorectal cancer (MSI-H or dMMR), and liver cancer
Pembrolizumab (KEYTRUDA)	Merck	PD-1	IgG-4	2014	Melanoma, non-small cell lung cancer, head and neck squamous cell carcinoma, classic Hodgkin's lymphoma, urothelial carcinoma, MSI-H tumor, and gastric cancer
Atezolizumab (Tecentriq)	Roche	PD-L1	IgG-1	2016	Urothelial cancer, non-small cell lung cancer

Generic Name (Trade Name)	Company	Target	Category	Time of Marketing	Current Indication(s)
Durvalumab (Imfinzi)	AZ	PD-L1	IgG-1	2017	Urothelial carcinoma
Avelumab (Bavencio)	Merck & Pfizer	PD-L1	IgG-1	2017	Merkel cell carcinoma

As of 27 Sep., 2017

2.3 Scientific Rationale

2.3.1 Basis of SHR-1210 combined with apatinib in the second-line treatment of SCLC

Peripheral blood mononuclear cells (PBMCs) in SCLC patients show that there are more effector T cells in LD-SCLC patients than in ED-SCLC patients. SCLC patients with a long survival have a high ratio of effector T cells to regulatory T cells^[30]. In the phase I study of nivolumab 1, 3, and 10 mg/kg dose groups for the treatment of SCLC, the ORRs were 6%, 27%, and 17%, respectively, and the 24-week PFS rates were 25%, 44%, and 31%, respectively^[31,32]. The CheckMate 032 study is a phase I/II open-label study comparing the ORRs of nivolumab 1 mg/kg, nivolumab 1 mg/kg combined with anti-CTLA-4 monoclonal antibody ipilimumab 3 mg/kg, and nivolumab 3 mg/kg combined with ipilimumab 1 mg/kg in SCLC patients who have previously undergone first-line or second-line standard treatment. The results showed that, regardless of PD-L1 expression, ORRs were 10%, 23%, and 19%, respectively; mPFSs were 1.4, 2.8, and 1.4 months, respectively; mOSs were 5.7, 7.7, and 7.2 months, respectively; and the 1-year OS rates were 33%, 43%, and 35%, respectively. Common adverse events included asthenia, diarrhea, vomiting, skin rash, and serum lipase increased. The incidence of Grade ≥ 3 adverse events in the combination group was greater than that in the monotherapy group^[33]. The KEYNOTE 028 study is a phase Ib study evaluating pembrolizumab 10 mg/kg Q2W monotherapy as second-line treatment of advanced solid tumors. In SCLC patients with high PD-L1 expression, the ORR was 29.2% and the mPFS was 1.8 months. Common adverse events included joint pain, faintness, skin rash, diarrhea, and asthenia. The incidence of Grade ≥ 3 toxicity was 8.3%, with 1 case of enteritis resulted in death^[34].

In vivo studies have shown that very early angiogenesis is caused by the imbalance of angiogenesis and anti-angiogenic mediators. Multiple factors, overlapping signal pathways and mechanisms are involved in angiogenesis. Hypoxia during tumor growth stimulates angiogenesis by inducing the production of VEGF. The binding of VEGF and VEGFR activates the VEGF signaling pathway. Fibroblast growth factor (FGF) and angiopoietin-2 continuously stimulate angiogenesis. Therefore, the angiogenesis signaling pathway plays a vital role in the process of SCLC metastasis^[35].

The phase I clinical study of ramucirumab combined with pembrolizumab in the first-line, second-line, and subsequent lines of treatments of gastric cancer (including gastroesophageal junction tumors) showed ORRs of 14% (4/28) and 7% (3/4), respectively, mPFSs of 5.6 (95% CI: 2.4-NR) months and 2.6 (95% CI: 1.5-4.2) months, respectively, and 6-month PFS rates of 35% and 26.1%, respectively; in the second-line and subsequent lines of treatment, the mOS was 6.2 (95% CI: 4.4-12.6) months. The safety and tolerability were similar to those of monotherapies. Grade ≥ 3 adverse events included asthenia, hypertension, and enteritis, without additional toxicity^[36]. The phase II study in naive patients with metastatic renal carcinoma compared the efficacy and safety of atezolizumab combined with bevacizumab vs. atezolizumab monotherapy vs. sunitinib monotherapy, with the subjects in the atezolizumab monotherapy and sunitinib monotherapy groups crossing over to the atezolizumab combined with bevacizumab group for continued treatment after progressive disease assessment per RECIST v1.1. The results showed that the combination group was superior to the sunitinib group. Although atezolizumab monotherapy and sunitinib monotherapy had limited efficacy, the subjects still benefited after crossover to the combination group. The overall ORR of the crossover group was 26% (28% in the sunitinib group and 24% in the atezolizumab group), and the total mPFS was 8.8 months; the safety was consistent with the monotherapy and combination therapy groups. Grade ≥ 3 adverse events included asthenia, arthralgia, nausea, proteinuria, diarrhea, and vomiting^[37]. Currently, studies evaluating the efficacy and safety of VEGF/VEGFR inhibitors combined with immune checkpoint inhibitors combined with or without chemotherapy have been carried out in multiple tumors such as NSCLC and SCLC.

Apatinib mesylate (trade name: Aitan®) was developed by Jiangsu Hengrui Pharmaceuticals Co., Ltd. and was approved for marketing by the China Food and Drug Administration (CFDA; now National Medical Products Administration, or NMPA) in 2014. Apatinib is a small molecular targeted drug and exerts anti-angiogenic effect to treat cancer by inhibiting VEGFR. Recombinant humanized anti-PD-1 monoclonal antibody injection (SHR-1210), a new class 1 therapeutic biological product developed by Jiangsu Hengrui Pharmaceuticals Co., Ltd., has not been marketed both in China and abroad. Jiangsu Hengrui Pharmaceuticals Co., Ltd. has initiated Phase I/II clinical studies of SHR-1210 in several types of tumors in both Australia and China, and preliminarily validated the safety, tolerability and efficacy of SHR-1210 monotherapy in the treatment of advanced solid tumors.

Considering the role of immune-related therapies in SCLC, as well as the role of immune checkpoint inhibitors combined with VEGF and VEGFR-2 inhibitors in patients with gastric cancer and kidney cancer, the benefits of SHR-1210 combined with apatinib in the second-line treatment of SCLC are reasonable and worth looking forward to.

2.3.2 Basis for SHR-1210 administration at the fixed dose of 200 mg

PD-1 immune checkpoint inhibitors exert their effect on immunosuppression by blocking the binding of PD-1/PD-L1. Therefore, the receptor occupancy of these inhibitors is the basic pharmacological mechanism that reflects the ultimate anti-tumor effects. Phase I PK studies showed that, serum drug concentrations dropped below 1000 ng/mL on Day 15 after a single dose of SHR-1210 1 mg/kg and a fixed dose of 60 mg, and remained between 4000-9000 ng/mL after a single dose of 3 mg/kg and a fixed dose of 200 mg. Receptor occupancy assays suggest that to maintain the receptor saturation, a serum drug concentration of at least 2000 ng/mL is required. Clinical data also suggest that a fixed dose of 200 mg every 2 weeks can maintain a saturated receptor occupancy. In Phase I studies, the incidence of adverse events did not increase with dose, whether the drug was administered by weight or by a fixed dose. Based on results from the studies described above, and taking into account the convenience of clinical administration, a fixed dose of 200 mg Q2W was selected.

2.3.3 Basis for continued medication beyond progression

Increasingly more clinical evidence shows that, after immunostimulant therapy in some patients, progressive disease (through traditional response evaluation, per RECIST v1.1) precedes objective clinical response and/or stable disease. This phenomenon was observed in approximately 10% of patients in the phase I study of nivolumab^[38]. Two hypotheses attempt to explain this phenomenon. One is that the enhanced inflammatory response in the tumor leads to an increase in the size of the tumor. Over time, the seemingly worsening part and the inflammatory part disappear, and the therapeutic effect begins to appear. The other is that the growth rate of tumors exceeds the rate of immune anti-tumor. After a sufficiently long period of time, the anti-tumor activity finally dominates and the therapeutic effect begins to appear. Therefore, subjects who are clinically evaluated as beneficial and well tolerated are allowed to undergo immune checkpoint inhibitors again after the initial progressive disease as defined per RECIST v1.1. Such subjects shall discontinue the study treatment after relapse of progressive disease.

2.3.4 Basis for selecting PD-L1 as the exploratory biomarker

As described in 2.2.2 of the protocol, PD-L1 is up-regulated in a variety of solid tumors. PD-L1 expression is closely related to shortened survival and poor prognosis in various cancers, including lung cancer, liver cancer, gastric cancer, esophageal cancer, urothelial cancer, renal cancer, pancreatic cancer, and ovarian cancer^[28]. In *in vitro* studies, tumor cells expressing PD-L1 promote the apoptosis of activated tumor cell-specific T cells, while tumor cells avoid the killing effect of effector T cells. In a number of clinical studies of nivolumab and pembrolizumab, the expression level of PD-L1 in tumor tissues was positively correlated with the efficacy. Based on the above evidence, the expression level of PD-L1 in tumor tissues may be related to the efficacy of SHR-1210, and preliminary biomarker exploration is necessary.

2.4 Preclinical Studies

Refer to Investigator's Brochure (IB) (version number: 2.0, version date: 24 Nov., 2016) for the pharmacology studies, toxicology studies, and pharmacokinetics studies of SHR-1210. Refer to IB (version number: 2.0, version date: 8 Dec., 2016) for the pharmacokinetics studies, toxicology studies, and pharmacokinetics studies of apatinib mesylate tablets.

2.5 Clinical Studies

Refer to the IB of SHR-1210 (version number: 2.0, version date: 24 Nov., 2016) and the IB of apatinib mesylate tablets (version number: 2.0, version date: 8 Dec., 2016).

2.6 Potential Risks and Benefits

Only topotecan (intravenously or orally administered) has been approved by the FDA for the treatment of ED-SCLC after failure of first-line standard therapies. No immunotherapy is commercially available currently. SHR-1210 is a humanized PD-1 antibody independently developed by Hengrui. Preclinical data suggested that it has similar pharmacodynamics and anti-tumor effects to nivolumab and pembrolizumab. The studies on the PD-1/PD-L1-based combination therapy that have been published and undergoing abroad suggest that patients may benefit and the safety is controllable. For more detailed safety information of SHR-1210, please refer to the IB (version number: 2.0, version date: 24 Nov., 2016) and the informed consent form (ICF).

3 STUDY OBJECTIVES AND ENDPOINTS

3.1 Study Objectives

3.1.1 Primary objective

- To evaluate the safety and efficacy of SHR-1210 combined with apatinib in the treatment of ED-SCLC failing first-line standard therapy

3.1.2 Secondary objective

- To evaluate the immunogenicity

3.1.3 Exploratory objective

- To evaluate the correlation between biomarkers (including but not limited to PD-L1 and TMB) and efficacy

3.2 Study Endpoints

3.2.1 Primary endpoints

- Incidence of AEs evaluated per CTCAE 4.03, especially the incidence of AEs meeting any of the following criteria:
 - Hematologic toxicity
 - Grade 4, or
 - Grade ≥ 3 thrombocytopenia with hemorrhage, or
 - Grade ≥ 4 neutropenia with pyrexia and infection
 - Grade ≥ 3 non-hematologic toxicity (except for laboratory abnormalities), hypertension, rash, diarrhea, nausea and vomiting that cannot be controlled after symptomatic treatment
 - Grade ≥ 3 laboratory abnormalities that lead to medical interventions or hospitalization, or last for ≥ 7 days
 - Any Grade 5 AEs
- ORR evaluated as per RECIST v1.1

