8.2 Safety Evaluation

8.2.1 Routine laboratory safety evaluation

Table 15. Routine laboratory safety evaluation

Hematology	RBC, HGB, HCT, WBC, PLT, LYM, ANC, MONO, EOS, and BASO
Coagulation Function	TT, PT, APTT, and INR
Clinical Chemistry	TBIL ^a , ALT, AST, γ -GT, ALP, ALB, TP, LDH, BUN, Cr, Na, K, Cl, Mg, Ca, P, lipase, amylase, and FBG
Urinalysis	PH, UALB, UPRO ^b , URBC ^c , and UGLU
Routine Stool Test	Occult blood

^a. If TBIL $\geq 2 \times$ ULN (without evidence of Gilbert syndrome), then direct bilirubin and indirect bilirubin shall be tested separately.

^b. The white blood cells should be examined microscopically (if appropriate), and the red blood cells should be examined with a high-power field of view.

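### The neutropenia line in the highlighted list of the primary safety endpoint is redundant at Grade ≥ 4, so complicated Grade 3 neutropenia enters that list only if another line happens to catch it

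*Protocol*

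**What the plan says.** Protocol 3.2.1 defines the primary safety endpoint as "Incidence of AEs evaluated per CTCAE 4.03, especially the incidence of AEs meeting any of the following criteria". The list that follows works as an any-of rule. Its lines are:

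- hematologic toxicity, first line: Grade 4, with no further condition;
- hematologic toxicity, second line: "Grade ≥ 3 thrombocytopenia with hemorrhage, or";
- hematologic toxicity, third line: Grade ≥ "4 neutropenia with pyrexia and infection";
- non-hematologic: "Grade ≥ 3 non-hematologic toxicity (except for laboratory abnormalities), hypertension, rash, diarrhea, nausea and vomiting that cannot be controlled after symptomatic treatment";
- laboratory: "Grade ≥ 3 laboratory abnormalities that lead to medical interventions or hospitalization, or last for ≥ 7 days";
- fatal: "Any Grade 5 AEs".

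SAP 4.1 (Primary Endpoints) repeats the list with the same neutropenia threshold. SAP 5.5.1 (Adverse events) repeats it again and says that the incidences and outcomes of these events are analyzed separately. The severity table in Protocol 9.1.2 ends at Grade 5, which is death.

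**The concern.** The second hematologic line lets a complication bring a Grade 3 cytopenia into the list. The third line has the same form, a cytopenia plus a complication, but starts at Grade 4. From that grade upward the list already counts everything, so the fever-and-infection condition can never decide whether an event is counted.

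What is at stake is the reported incidence of the highlighted subset, which the SAP analyzes on its own. A reader of that table would reasonably think that complicated neutropenia has a dedicated route into it. For Grade 3 neutropenia there is none. Whether such an event is counted depends on how two other lines are read, and the plan leaves one of those readings open.

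**Working it through.** The documents state no figure on this point, so there is none to reproduce. The check is one of logic.

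**Step 1: redundancy.** The scale stops at 5, so Grade ≥ 4 means Grade 4 or Grade 5.

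- Grade 4 neutropenia with fever and infection is a Grade 4 hematologic toxicity, so the first hematologic line counts it.
- Grade 5 neutropenia with fever and infection is a Grade 5 event, so the fatal line counts it.

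Hence {neutropenia line} ⊂ {hematologic Grade 4} ∪ {any Grade 5}, and the increment to the combined count is 0.

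**Step 2: enumeration.** A neutropenia event is described by:

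- its grade, 1 to 5 (5 values);
- fever and infection: absent; present with the infection below Grade 3; or present with the infection at Grade ≥ 3 (3 values);
- intervention, hospitalization or duration ≥ 7 days: yes or no (2 values);
- whether neutropenia is read as a laboratory abnormality: yes or no (2 values).

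That gives 5 × 3 × 2 × 2 = 60 combinations.

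| Threshold in the neutropenia line | Combinations flagged by that line alone |
|---|---|
| Grade ≥ 4 (as written) | 0 of 60 |
| Grade ≥ 3 (parallel to thrombocytopenia) | 3 of 60 |

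**Step 3: Grade 3 neutropenia with fever and infection under the list as written.** There are 2 × 2 × 2 = 8 combinations.

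| Infection itself Grade ≥ 3 | Neutropenia read as laboratory abnormality | Intervention, hospitalization or ≥ 7 days | In the list? |
|---|---|---|---|
| yes | either | either | yes, non-hematologic line (4 combinations) |
| no | yes | yes | yes, laboratory line (1) |
| no | yes | no | no (1) |
| no | no | either | no (2) |

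Caught: 4 + 1 = 5 of 8. Not caught: 1 + 2 = 3 of 8. These three are the same three that the Grade ≥ 3 threshold adds in Step 2.

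**Step 4: how firm the laboratory route is.** Protocol 8.2.1 lists ANC among the routine hematology parameters ("RBC, HGB, HCT, WBC, PLT, LYM, ANC, MONO, EOS, and BASO"), which supports reading neutropenia as a laboratory abnormality. Against that, Protocol 3.2.1 gives hematologic toxicity a line of its own and does not say whether such events may also qualify under the laboratory line. Nor does it say whether treating the infection counts as an intervention to which the neutropenia led.

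The enumeration assumes that a Grade ≥ 3 infection meets the non-hematologic line. If the closing condition of that line, about control by symptomatic treatment, were read as applying to every toxicity named in it, fewer cases would be caught.

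**The case against.** The strongest reply is that little is lost.

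- **The endpoint is all AEs.** The list is introduced as an emphasis within that endpoint. A reader might infer that complicated Grade 3 neutropenia is left out of the primary safety endpoint. The documents do not support that: the event always counts there and can only fall outside the highlighted subset.
- **Other lines may catch it.** A neutropenic subject with fever and infection may well be treated or hospitalized, which can bring the laboratory line into play. To say flatly that such events are missed would go too far.
- **The events are reported elsewhere.** Protocol 10.5.4 summarizes Grade ≥ 3 AEs. SAP 5.5.1 provides for Grade ≥ 3 TEAE summaries and a listing of all AEs.
- **Stage I does not use the list.** A reader might infer that the Stage I view of tolerability is understated. SAP section 6 bases that review on listings of AEs and laboratory evaluations, and Protocol section 4 ties the choice of group to no criterion in this list. The event, its grade and the ANC value would be in view.
- **The line can still be tabulated.** Because the listed events are analyzed separately, it can serve as a sub-count of complicated Grade 4 or 5 neutropenia. Deleting it would also remove the redundancy.

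All of this stands and limits the consequence. It does not make the line add anything to the combined count, and it does not settle whether neutropenia falls under the laboratory line. The intended threshold is inferred from the parallel thrombocytopenia line; the documents do not state it.

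**Conclusion.** The point holds as a defect in the definition of the highlighted subset. As written, the neutropenia line adds exactly 0 events to the combined count; this follows from the text and needs no assumption. Grade 3 neutropenia with fever and infection enters the subset only when the infection is itself Grade ≥ 3, or when neutropenia counts as a Grade ≥ 3 laboratory abnormality with intervention, hospitalization or duration ≥ 7 days. That the threshold is a slip is a well-supported inference, not a certainty.

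The effect is confined to the reported incidence of the highlighted events. It cannot be turned into a number of subjects, because the documents give no rate for such events and do not settle how often the laboratory line would apply. No sample size, significance level or power figure depends on the list, and the only numerical go/no-go rule is the response count of at least 9 in 40 (Protocol 10.1, SAP 2.3). The change is still worth making: the list is part of a primary endpoint, the SAP analyzes it separately, and the edit costs almost nothing.

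**What to change.** Before database lock, by which time Protocol 10.2 requires the SAP to be final, make two changes together in Protocol 3.2.1, SAP 4.1 and SAP 5.5.1:

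1. In the neutropenia line, replace ≥ 4 by ≥ 3 and leave the rest of the line as it is, so that it parallels the thrombocytopenia line.
2. Add one sentence saying whether a hematologic toxicity may also qualify under the laboratory-abnormality line. If it may, say whether treatment or hospitalization for the accompanying infection counts as a consequence of the neutropenia.

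The second change is needed even with the first, because the new threshold alone leaves the laboratory line open to two readings. Both concern how events are classified for analysis, not how subjects are treated.

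The cost is the same one-character edit in three places plus one sentence, with no new data to collect. The downside is that the reported incidence of highlighted events may be slightly higher.
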